7.6.2 Serology

A test for hepatitis B surface antigen, hepatitis C virus and human immunodeficiency virus (anti-HIV1/2) will be performed at Screening. In case of positive results, the subject will be referred to appropriate medical care.

7.6.3 Urine Drug Screen

A urine drug screen will be performed at the site at Screening and Admission. The urine will be screened for amphetamine type substances, barbiturates, benzodiazepines, cannabinoids, cocaine and opiates.

7.6.4 Urine Cotinine Screening

A urine dip-stick cotinine test will be performed at Screening in order to confirm the subject's smoking status. The test must detect cotinine with a threshold of ≥ 200 ng/mL, (e.g., One-Step Cotinine Test 008A086, Ultimed, Belgium).

7.6.5 Alcohol Breath Test

An alcohol breath test will be conducted using an alcometer device at Screening and Admission.

Confidentiality Statement

Data and information contained in this document are considered to constitute trade secrets and confidential commercial information, and the legal protections provided to such trade secrets and confidential information are hereby claimed under the provisions of applicable law. No part of this document may be publicly disclosed without the written consent of Philip Morris Products S.A.

7.6.6 Urine Pregnancy Test

A urine pregnancy test will be performed for all female subjects at Screening, Admission and at Discharge. Subjects with a positive urine pregnancy test at the Screening or Admission Visits will not be enrolled and will be considered as screen failures. In case of any positive pregnancy test, the Investigator or designee will inform the subject about the risks associated with smoking during pregnancy.

All pregnancies detected during the study must be reported and handled as described in section 8.5.

7.7 Sample Handling, Storage, and Shipment

Participating laboratories for blood samples testing and safety laboratory samples testing are listed in Appendix B. Urine drug screen, breath alcohol screen, urine pregnancy tests and urine cotinine tests will be done by the site personnel at the site.

Detailed procedures for handling of samples are described in the separate sample handling manual (SHM). Safety laboratory samples will be destroyed as per laboratory local regulations. All other samples will be destroyed post database lock or post finalization of the bioanalytical reports, whichever occurs last. The facility/-ies at which the samples are stored will be informed in writing by the Sponsor when destruction of the samples shall be performed.

7.7.1 Blood Samples

Blood samples will be drawn by qualified and trained site personnel. Since the test for nicotine concentration is highly sensitive, precautions should be taken during blood sampling and processing to prevent the contamination of samples with environmental nicotine. Subjects should be in a seated position during blood collection.

In total, around 464 mL will be drawn for this study including samples for determination of nicotine concentrations, CYP2A6 activity and safety. This calculation is based on an individual volume of each sample of 5 mL for nicotine PK (of which 4 mL is needed for nicotine dosing and 1 mL for cannula rinsing of saline solution as per site's SOPs), 4 mL for CYP2A6 analysis and 12.5 mL for safety laboratory assessments. The total volume of blood drawn will not exceed the levels for a standard blood donation.

More details on the procedures for collection, labeling, handling and shipment of samples are described in a separate SHM.

7.8 Questionnaires

The subject questionnaires will be completed by the subjects directly following both fixed puffing and *ad libitum* use. The questionnaires will be reviewed for completeness by the study site collaborator and subjects will be requested to complete any missing information.

Confidentiality Statement

Data and information contained in this document are considered to constitute trade secrets and confidential commercial information, and the legal protections provided to such trade secrets and confidential information are hereby claimed under the provisions of applicable law. No part of this document may be publicly disclosed without the written consent of Philip Morris Products S.A.

Symptoms or worsening of symptoms as documented on any of the questionnaires do not need to be documented as AEs because the questionnaires will be analyzed as part of the report. However, it is at the discretion of the Investigator to document such symptoms also as AEs. The main source for AE collection will be the face-to-face interview between the subject and investigational site staff using, open, non-directive questions (see section 8.2.1).

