6.2.4 Stopping Rules for Investigational Product

For safety purposes, use of P3P should be temporarily reduced (decreasing number or/and intensity of puffs) or stopped in the event of any signs suggesting nicotine overexposure, e.g., gastrointestinal disturbance (nausea, vomiting, diarrhea, stomach or abdominal pain), cold sweats, headache, dizziness and breathing problems, or any reasons at the discretion of the Investigator.

In the morning of Day 2 subjects will be randomized after confirmation that there are no safety concerns based on the Investigator's judgement.

For subjects who are discontinued, the reason for discontinuation should be documented in the source documents and in the CRF and subjects will undertake early termination procedures (section 9.6).

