8.2 Collection and Reporting of Adverse Events

8.2.1 Collection of Information

Any non-serious AE occurrence during the study must be documented in the subject's medical records in accordance with the Investigator's normal clinical practice and on the AE page of the CRF. SAEs that occur during the study must be documented in the subject's medical record, on the AE CRF, and on the SAE form.

AEs should be collected mainly via face-to-face interview with the subject through spontaneous reporting or by the use of consistent, open, non-directive questions from the investigator(s) or designee(s) (e.g., "Have you had any health problems since you were last asked? or "How have you been feeling since you were last asked?").

Information recorded will include: verbatim description of the AE/SAE, start and stop dates, seriousness, severity (intensity), action taken (e.g., whether or not the AE/SAE led to the subject's discontinuation from the study), and outcome (e.g., resolved, stabilized).

Information to be recorded about an AE/SAE should include, whenever possible, onset and resolution dates and times, circumstances leading up to the event, clinical elements such as clinical course, specific vital signs and test results that may explain the pathophysiology of the event, as well as alternative explanations to its occurrence.

Whenever a medically meaningful diagnosis is available to comprise a set of reported signs and/or symptoms, it should be preferentially provided as the AE or SAE term, rather than the individual signs and/or symptoms. Otherwise, each one of those signs and/or symptoms should be reported separately as event terms.

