In general, all safety data will be listed and tabulated using the approach described in section 12.1.3. Safety variables collected during exposure periods will also be reported by product exposure.

AE data will serve for the primary assessment of safety. Other safety variables monitored in this study include: incidence and frequency of P3P product events including malfunction/misuse; respiratory symptoms (cough assessment VAS and Likert scales); vital signs (systolic and diastolic blood pressure, pulse rate, respiratory rate); spirometry; ECG data; clinical chemistry, hematology, and urine analysis safety panel; physical examination; concomitant medications.

All safety data will be listed and AEs will be summarized by product variant (fixed puffing regimen and *ad libitum* use periods will be combined at the product variant level). Safety measurements assessed both after fixed puffing regimen and *ad libitum* use (vital signs, ECG etc.) will be summarized per fixed puffing/*ad libitum* use regimen and product variant.

Confidentiality Statement

Data and information contained in this document are considered to constitute trade secrets and confidential commercial information, and the legal protections provided to such trade secrets and confidential information are hereby claimed under the provisions of applicable law. No part of this document may be publicly disclosed without the written consent of Philip Morris Products S.A.

The number and percentage of subjects with AEs, SAEs, and product events will be tabulated by system organ class and preferred term. Summaries will also be presented for AEs leading to discontinuation, AEs leading to death, AEs by relatedness to product exposure (with and without laboratory related AEs), AEs by severity, and laboratory AEs. Tabulations will be performed for both the number of subjects experiencing an event and the number of events.

Safety laboratory assessments are performed on Day 2 to Day 5 in the morning prior to product use (Appendix A). Any lab related AEs will be assigned to the product used on the previous day.

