**Table 8 Adapted mCEQ - Questions and Subscales**

Question	Subscale
1 Was it satisfying?	Product Satisfaction
2 Did it taste good?	Product Satisfaction
3 Did you enjoy the sensation in your throat and chest?	Enjoyment of Respiratory Tract Sensations
4 Did it calm you down?	Psychological Reward
5 Did it make you feel more awake?	Psychological Reward
6 Did it make you feel less irritable?	Psychological Reward
7 Did it help you concentrate?	Psychological Reward
8 Did it reduce your hunger for food?	Psychological Reward
9 Did it make you dizzy?	Aversion
10 Did it make you nauseated?	Aversion
11 Did it immediately relieve your craving for a cigarette?	Craving Reduction
12 Did you enjoy it?	Product Satisfaction

The subscales scores will be derived by averaging the relevant individual non-missing item scores if at least 50% are non-missing, otherwise the subscale score will be set to missing.

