#### Confidentiality Statement

Data and information contained in this document are considered to constitute trade secrets and confidential commercial information, and the legal protections provided to such trade secrets and confidential information are hereby claimed under the provisions of applicable law. No part of this document may be publicly disclosed without the written consent of Philip Morris Products S.A.

Nicotine PK parameters will be derived from plasma nicotine concentrations versus time data by non-compartmental analysis (NCA) and any required data transformation for the PK analysis on the provided analysis PK set will be conducted using Phoenix® WinNonlin® version 7.0 or higher (Certara L.P. (Pharsight), St. Louis, MO).

Data listings will be provided for all data collected as required by the protocol, and including all data derived for analysis purposes, ordered by subject, product variant (if applicable), use regimen (if applicable) and time point (if applicable), unless otherwise stated. Data listings will include all subject level data collected unless otherwise specified.

Summary statistics and statistical analysis will only be presented for data where detailed in this SAP.

Safety data will be summarized for the Safety Population. All endpoints other than safety will be analyzed using the PK population.

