### **12.6.2.2.2 Adapted Modified Cigarette Evaluation Questionnaire**

The adapted mCEQ subscale scores will be summarized by P3P variant (Table 15.2.4.9). The answers to the individual questions along with the scores will also be listed (Listing 15.3.4.5). Boxplot of adapted mCEQ subscale scores by P3P variant will be presented (Figure 15.1.4.7).

A mixed model will be conducted for the adapted mCEQ subscale scores with fixed terms for sequence, product variant and two dummy variables for Day 3 and Day 4 (i.e two variables taking value 1 for Day 3 and Day 4 respectively and value 0 for the other study days) and using subject nested within sequence as random effect. In this way Day 1 and Day 2 will be combined to address the multicollinearity as planned in the protocol. The SAS code to be used is shown below:

```
proc mixed data=_data_;  
  class Sequence Product_Variant Day3 Day4 Subject;  
  model mCEQ_Subscale_Score = Sequence Product_Variant Day3 Day4 / ddfm=SAT s;  
  random Subject(Sequence) / sub=Subject type=CSH;  
  lsmeans Product_Variant / cl diff alpha=0.05;  
run;
```

In case of model convergence issues, this will be reported in the study report and the variance component (type=VC) covariance structure will be investigated.

Least square means and differences will be presented for the analysis of the adapted mCEQ subscale scores together with 95% confidence interval for the following effects of interest (Table 15.2.4.10):

- P3P 2 vs P3P 3, to describe the effect of an increase of nicotine powder concentration from 2.5% to 5%
- P3P 2 vs P3P 4, to describe the effect of a decrease from 2.25  $\mu$ m to 1.8  $\mu$ m of the median particle size in the nicotine powder
- P3P 2 vs P3P 1, to describe the effect of flavor

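### Protocol 7.8 excuses questionnaire symptoms from AE recording because the questionnaires are analysed, but the planned mCEQ analysis does not give the incidence of dizziness or nausea

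*Protocol*

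**What the plan says.** **AE recording.** Protocol 7.8 says: "Symptoms or worsening of symptoms as documented on any of the questionnaires do not need to be documented as AEs". The reason it gives is that the questionnaires will be analysed for the report. The Investigator may still record them as AEs, and the main AE source is a face-to-face interview with open questions. Protocol 8.1.1 counts an unfavourable symptom as an AE, subject to the Investigator's medical judgement. Protocol 8.2.1 adds: "Any non-serious AE occurrence during the study must be documented in the subject's medical records". Protocol 12.6.3 says: "AE data will serve for the primary assessment of safety".

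**The symptoms.** Protocol 6.2.4 lists these signs suggesting nicotine overexposure: "gastrointestinal disturbance (nausea, vomiting, diarrhea, stomach or abdominal pain), cold sweats, headache, dizziness and breathing problems". SAP Table 8 includes a dizziness question (item 9) and a nausea question (item 10), each scored from 1 (not at all) to 7 (extremely). Under Protocol 7.8.3 the mCEQ is completed within 60 minutes after the ad libitum session on Days 1 to 4.

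**The analysis.** Items 9 and 10 form the Aversion subscale. SAP 7.3.3 says: "The subscales scores will be derived by averaging the relevant individual non-missing item scores", provided at least half are present. SAP 12.6.2.2.2 summarises, box-plots and models subscale scores (Tables 15.2.4.9 and 15.2.4.10, Figure 15.1.4.7) and sends item answers to Listing 15.3.4.5. On populations, SAP 12.1 says: "All endpoints other than safety will be analyzed using the PK population".

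**The concern.** The waiver in Protocol 7.8 gives one reason: the questionnaires are analysed anyway. That reason is sound only if the analysis shows what the AE record would have shown, namely how many subjects had the symptom on each variant. For dizziness and nausea it does not.

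At stake is how tolerability by variant is read. Safety and tolerability is a stated secondary objective (Protocol 3.2). The study compares 2 mg variants with a 1 mg variant, and Protocol 2.1.2 says there are no human data on nicotine absorption from P3P. Ad libitum use has no limit on puffs or products (Protocol 6.2.2), and the mCEQ is the only instrument that asks every subject directly about these two symptoms after it. With 18 randomized subjects, a few cases on one variant matter, and a reader of the tables could not count them.

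**Working it through.** The plan states no figure on this point, so there is none to reproduce. The check follows the two items from collection to output, then asks what the Aversion score retains.

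**1. Path to the AE tables.** SAP Tables 15.2.6.1 to 15.2.6.8 are built from AE records. A symptom marked on the mCEQ is absent from them if both of these hold:
- the subject does not report it at the open-question interview;
- the Investigator does not use the discretion in Protocol 7.8 to record it.

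**2. Path to the mCEQ tables.** Aversion score = (item 9 + item 10) / 2. If one item is missing, 1 of 2 is 50%, so the score is the other item alone. The tables use the PK population, and subjects with major deviations that affect evaluability are removed from it (SAP 10.4).

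**3. Can item incidence be recovered?** There are 7 × 7 = 49 answer pairs. Their sums run from 2 to 14, which gives 13 scores.

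| Aversion score | Pairs giving it |
|---|---|
| 1.0 | 1 |
| 2.5 | 4: (1,4), (2,3), (3,2), (4,1) |
| 4.0 | 7 |
| 7.0 | 1 |

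Only 1.0 and 7.0 identify both answers.

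**4. Illustration with assumed answers, 18 subjects.** Twelve answer (1,1). The other six all give one of the pairs below (dizziness first).

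| Pair for the six | Aversion mean | Median | Dizziness above 1 | Nausea above 1 |
|---|---|---|---|---|
| (4,1) | 1.5 | 1.0 | 6 | 0 |
| (2,3) | 1.5 | 1.0 | 6 | 6 |
| (1,4) | 1.5 | 1.0 | 0 | 6 |

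Mean = (12 × 1.0 + 6 × 2.5) / 18 = 27/18 = 1.5. The 18 scores are the same in all three rows, so every summary statistic and the boxplot are the same too.

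**5. What the summaries can still show.** Suppose four subjects answer (7,1) and fourteen answer (1,1).
- Each of the four scores (7 + 1) / 2 = 4.0.
- Mean = (4 × 4 + 14 × 1) / 18 = 30/18 = 1.67, against 1.00 with no symptoms.
- SD = √(28/17) = 1.28 and maximum = 4.0, against 0 and 1.0.
- The item count would be 4/18 = 22% with extreme dizziness (exact 95% CI 6.4% to 47.6%).

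The spread and the maximum show that something occurred. They do not show which symptom: a 4.0 could equally be (1,7) or (4,4).

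**6. Other questionnaires in the same plan.** The waiver also covers cough. Yet SAP 12.6.5.5.6 gives the number and percentage of subjects reporting cough, and Table 15.2.6.19 uses the Safety population. The Sensory Questionnaire is analysed item by item (SAP 7.3.4).

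**The case against.** **The interview route is real.** Protocol 8.2.1 makes the interview the main AE source, and 7.8 does not excuse a symptom reported there. Subjects are supervised continuously during use (Protocol 6.2.2). Reduced, interrupted or stopped product use is an AE action category (SAP Table 13), and it is tabulated. This stands: the loss is possible, not certain. A reader might infer that the AE tables will understate these symptoms; the documents do not show that.

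**No flat contradiction.** A reader might infer that 7.8 simply overrides 8.1.1 and 8.2.1. But 8.1.1 calls for medical judgement on what is a true AE, and 7.8 leaves questionnaire symptoms to that discretion. What remains is a tension: 7.8 rests its waiver on the analysis, not on judgement, while 8.2.1 requires documentation.

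**Subjects outside the PK population.** It is tempting to say they appear in no table. They are absent from the mCEQ tables only. An exposed subject with a post-exposure safety assessment is in the Safety population (SAP 10.5), and any AE recorded for that subject is tabulated. The population gap is also narrow, because one completed use and one derivable primary PK parameter suffice for inclusion.

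**More than means is planned.** SAP 12.1.3 adds SD, median, quartiles, minimum and maximum, and boxplots are planned. This also stands, as step 5 shows. It does not restore an incidence for either symptom.

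**The mCEQ is a pharmacodynamic endpoint and cough is a safety endpoint.** That explains the different populations. It does not supply the analysis on which 7.8 relies.

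**Conclusion.** The point holds as a reporting gap. The analysis that Protocol 7.8 gives as its reason for not requiring AE records yields no count of subjects with dizziness or nausea on any variant, and none can be derived from the Aversion summaries. The raw answers survive in Listing 15.3.4.5, but a listing is not a tabulated incidence.

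The size is unknown. Of the symptoms marked on the mCEQ, the share missing from the AE tables could be anything from none to all, because the documents do not say how many subjects would also report them at interview. The 18-subject examples use assumed answers. They show what the score can conceal and predict nothing about this study. Nor do the documents support calling this the first human use of the 2 mg variants; Protocol 2.1.2 says only that human nicotine-absorption data are lacking.

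The study is descriptive and makes no claim from its intervals, so this is an inexpensive improvement to the readability of tolerability by variant. It does not threaten the primary PK objective.

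**What to change.** **1. Add one table to SAP 12.6.5**, in the Safety population and by P3P variant, parallel to cough Table 15.2.6.19. For item 9 and item 10 separately, give the number and percentage of subjects at each score from 1 to 7, among those who answered the item for that variant. Two conditions apply:
- Label it as covering ad libitum use only. AE tables by variant combine fixed puffing and ad libitum use (Protocol 12.6.3), so the two are not like for like.
- Show the full distribution rather than a single cut-off above 1, since the documents justify no threshold.

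SAP section 3 allows additional analyses to be described in the CSR, so the table could also be added that way.

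**2. Reconcile Protocol 7.8 with 8.1.1 and 8.2.1** on whether symptoms reported on questionnaires are to be documented as AEs. Which text should give way is for the sponsor and the Investigator to settle.

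**Cost.** One extra table from data already collected, with no new visit or procedure, plus a clarification of wording. The downside is that scores of 2 or 3 may reflect trivial symptoms and could be over-read.

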7.8.1 Fagerström Test for Nicotine Dependence

Potential nicotine dependence will be assessed via a subject self-reported questionnaire at Screening using the Fagerström test for nicotine dependence (FTND) in its revised version (18).

The questionnaire consists of six questions that will be answered by the subject. The scores obtained allow the classification of nicotine dependence in three different levels: mild (0-3 points), moderate (4-6 points), and severe (7-10 points).

7.8.2 Visual Analogue Scale for Craving

A VAS-craving assessment will be used to assess the level of craving of the subject based on their response to the question, "How strong is your craving for cigarettes?" on a scale of 0 (no craving) to 10 (strong craving) (19).

The VAS craving will be completed by the subject at Days 1 to 4. For the fixed puffing regimen the first assessment will be done 15 minutes \pm 5 minutes prior to T_0 fix, all other assessments will be done after T_0 fix, at 4 minutes \pm 2 minutes, at 10 minutes \pm 2 minutes, at 15 minutes \pm 2 minutes, 30 minutes \pm 5 minutes, 1 hour, 2 hours, 4 hours \pm 10 minutes each.

For the *ad libitum* use period the first assessment will be done 15 minutes \pm 5 minutes prior to T_0 ad lib, all other assessments will be done after T_0 ad lib, at 10 minutes \pm 2 minutes, at 20 minutes \pm 2 minutes, 30 minutes \pm 5 minutes, 40 minutes \pm 5 minutes, 1 hour, 2 hours, 4 hours \pm 10 minutes each.

Questionnaires are to be completed after blood samples have been taken.

7.8.3 Adapted Version of the Modified Cigarette Evaluation Questionnaire

An adapted mCEQ will be completed by each subject within 60 minutes after the *ad libitum* use session on Days 1 through 4.

The questionnaire to be used adapts the wording of mCEQ items (20) to RRPs, following a similar approach with the Product Evaluation Scale (21) which is an adaptation of the mCEQ for oral tobacco products.

The questionnaire assesses the degree to which subjects experience the reinforcing effects of P3P use by measuring:

- Product satisfaction (satisfying, tastes good, enjoy the product).

Confidentiality Statement

Data and information contained in this document are considered to constitute trade secrets and confidential commercial information, and the legal protections provided to such trade secrets and confidential information are hereby claimed under the provisions of applicable law. No part of this document may be publicly disclosed without the written consent of Philip Morris Products S.A.

- Psychological rewards (calms down, more awake, less irritable, helps concentrate, reduces hunger).
- Aversion (dizziness, nausea).
- Enjoyment of respiratory tract sensations (single-item assessment)
- Craving reduction (single-item assessment)

